9.0 Data Analysis

- Startle Data Collection, Processing and Statistical Analysis: Stimuli will be administered using Presentation software (Albany, CA) and data collected using

Biosemi Actiview 2 system. Acoustic startle probes will be 40-ms duration, 103-dB bursts of white noise with near-instantaneous rise time presented binaurally through headphones. For the threat task, electric shocks will last 400-ms. Startle responses will be recorded and data collected and processed (e.g., filtering, rectification, smoothing, scoring blinks) according to published guidelines. The startle data will be processed using an interactive 'batch' program that the PI developed in BrainVision Analyzer (BrainProducts). The PI's data indicate that ~7% of blinks are "missing" and thus, we will administer a large number of startle probes (72) to ensure that missing responses do not bias analyses. Consistent with prior studies, we will create startle potentiation scores for U and P, which account for individual differences in baseline reactivity by subtracting responses during the N condition. All variables will be checked for inter- and intra-measure consistency, and frequency distributions will be examined for outliers. Data transformations will be employed as necessary.

- EEG Data Collection, Processing and Statistical Analysis: During the Alcohol Cue Reactivity task we will record continuous electroencephalography (EEG) readings using a 32 channel ActiveTwo BioSemi system (BioSemi, Amsterdam, Netherlands). The data is recorded off the scalp, non-invasively, while participants are wearing a stretch lycra EEG cap. The EEG signal will be pre-amplified at the electrode to improve the signal-to-noise ratio. The data will be digitized at 24-bit resolution with a Least Significant Bit (LSB) value of 31.25nV and a sampling rate of 1024Hz, using a low-pass fifth order sinc filter with a -3dB cutoff point at 204.8Hz. Off-line analysis will be performed using Brain Vision Analyzer software (Brain Products), using conventional preprocessing steps. Data will be re-referenced to the average of the two mastoids and high-pass (0.1Hz) and low-pass (30Hz) filtered. Data will be segmented around event markers that correspond to the administration of task stimuli. Baseline correction for each trial will be performed and brain activity averages will be computed for each condition, for each task.
- fMRI Data Collection, Processing and Statistical Analysis: All MR scanning will be performed on a 3.0 Tesla GE Discovery MR750 System (Milwaukee, WI) using a state-of-art 8-channel radiofrequency coil and updated software (Discovery 20.0, Neuro-optimized gradients), optimized to reduced susceptibility artifact in the ventral frontal cortex and medial temporal lobe. A high-resolution T1 scan (Bravo 3D IR-prepped fast SPGR: Axial 22 x 22cm FOV, 1mm slice thickness, 13° flip, TI = 450 ms, matrix = 256 x 256 matrix, 186 slices, NEX=0.75, 25kHz rBW, minimum TR/TE [~8-9ms/3-4ms]) will provide precise anatomical localization. Participants will be instructed on tasks and will be acclimated in an MRI simulator. Whole-brain fMRI BOLD-related signal measures will be acquired using a T2*-weighted echo-planar imaging sequence with BOLD contrast (gradient-echo axial EPI with 22 x 22cm FOV, 3 mm slice thickness, 0 gap, TR=2s, TE=minFull [~25ms], 90° flip, 250 kHz rBW, Parallel imaging (ASSET) =ON, Number of Slices: 43+ (optimal for normal coverage), 64 x 64 matrix) to measure task-related effects and designed to minimize susceptibility artifact (signal loss).

- Functional data will be processed and analyzed using conventional methods (GLM, event-related design, random effects) with Statistical Parametric Mapping (SPM8; Wellcome Department of Cognitive Neurology, London; www.fil.ion.ucl.ac.uk/spm). Analysis will implement two complementary approaches: 1) a hypothesis-driven, anatomically focused region of interest (ROI)-based analysis; and 2) exploratory whole-brain voxel-wise analysis.
- The Data Analysis Plan for each aim is presented in the “Statistical Considerations” section.

10.0 Quality Control and Quality Assurance

- Please see bullet below for description on how startle and fMRI data is evaluated for adherence with the protocol. As noted above, all self-report data will be double entered, checked for discrepancies, and cleaned. Analyses will assume that ‘missingness’ occurred at random, with data imputed when necessary. Type 1 error rates will be adjusted using Bonferroni corrections.
- The PI of the study and her research staff are responsible for the monitoring of the research and the evaluation of the data quality. After each session data is transferred to the lab storage drive. The data is closely reviewed to ensure its quality and that nothing is missing.
- Both startle and fMRI data are processed using automated scripts; however, the PI and study staff examine each blink file by hand to ensure acceptability and high-quality data.

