During the NPU task, BOLD is the index of stress reactivity. The BOLD contrasts of interest will capture activation during threat anticipation: U-threat anticipation > No-threat anticipation and P-threat anticipation > No-threat anticipation. At the end of the task, participants rate how intense, arousing, and anxiety provoking the conditions and shocks were. Of note, our prelim data from two separate studies indicate that despite being shocked, participants are able to remain still and total motion is minimal (n=237; M age=19.3; M translation=.03±.02mm and rotation=.02±.01degree across runs).

fMRI Lab Visits - Task 2: The Resting State Task (RST). For this task participants will view a fixation cross on a blank background for approximately 10 minutes. Participants will be instructed to keep their eyes open and focused on the cross, and to try not to think of anything in particular.

fMRI Data Processing. Data preprocessing will involve well-tested, routine procedures used in our lab. Conventional steps (e.g., realignment, normalization, smoothing) will be executed using Statistical Parametric Mapping software (SPM8; Wellcome Trust Center for Neuroimaging, London). Strict quality control procedures will be in place to evaluate head motion (e.g., excluding subjects with >1.5 mm movement in any direction) and ensure proper normalization. Motion parameters will be included in all

first-level models as regressors of no interest. Statistical analyses will use the modified General Linear Model (GLM) in combination with a temporal convolution for block-related analyses in a random effects model. Statistical inference will use random field theory to account for non-independent observations within a smooth map. We will implement 2 complementary approaches to test regional activation: 1) hypothesis-driven region-of-interest (ROI)-based analysis of BOLD percent signal change (PCS) created from anatomy-based landmarks using small-volume correction ($p < .05$, FWE-corrected); and 2) whole-brain activation search at a threshold of $p < .05$ (FWE-corrected).

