12.0 Statistical Considerations

13.0 Aim 1. Does a single dose of SUV decrease reactivity to U-threat? Hypothesis

1: Relative to PBO, SUV will acutely dampen startle reactivity to U-threat, but not P-threat. We will conduct a multilevel mixed model with startle magnitude as the dependent variable. Startle to U-threat and P-threat will be included as a within-subjects factor, to test for specific changes in U-threat. Time (baseline vs. acute challenge) and treatment arm (SUV vs. PBO) will be included as within-subjects and between-subjects factors, respectively, and we expect a time x treatment arm x task condition interaction on startle. Models will include a random effect for participant.

14.0 Aim 2. Does daily use of SUV decrease reactivity to U-threat? Hypothesis 2a:

4-weeks of SUV will result in greater reductions in reactivity to U-threat compared with PBO, and these changes will be specific to U-threat. Hypothesis 2b: SUV-related change in U-threat reactivity will be greatest amongst those with higher baseline U-threat reactivity. Exploratory Analysis: SUV will similarly result in decreases in aINS and dACC reactivity and connectivity during U-threat relative to PBO, and brain change will correlate with startle change. For H2a, we will conduct a multilevel mixed model that is nearly identical to the model described for H1. However, the time variable will be modeled as baseline vs. post-treatment. For H2b,

we will include baseline startle to U-threat as a predictor in our model and test for a baseline startle by treatment arm interaction. Lastly, for our exploratory fMRI analyses, we will first extract activation and functional connectivity parameter estimates from anatomical aINS and dACC during U-threat (and P-threat) > No-threat contrast maps. fMRI variables will be tested as dependent variables in the model used for H2a. Magnitude of brain change will be directly correlated with magnitude of startle change.

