15.0 Aim 3. Does daily use of SUV change alcohol behavior, and is this change linked to brain-behavior U-threat change? Hypothesis 3a: Daily SUV will result in greater reductions in PHDD and DPDD compared with PBO. **Hypothesis 3b:** SUV-related changes in PHDD and DPDD will be greatest in those with higher U-threat reactivity. **Hypothesis 3c:** In all subjects, changes in brain-behavioral U-threat reactivity will correlate with changes in drinking behavior. For H3a, linear mixed models will be used to assess the impact of treatment arm (SUV vs. PBO) on changes in drinking behavior over the 4-week follow-up period (daily reports). If the assumptions of linear models are violated due to skewed residual errors, we will explore the use of Poisson and negative binomial generalized linear mixed models to model drinking behavior. For H3b, baseline startle potentiation to U-threat (and in secondary models, aINS, dACC, and BNST parameter estimates) will be entered as a covariate/predictor and we will test for a baseline startle to U-threat by treatment arm interaction on drinking behavior outcomes. Lastly, the hypothesis for H3c will be tested using a linear mixed model that includes magnitude of U-threat and P-threat reactivity (startle and brain, separate models), time, and treatment arm as predictors and PHDD and DPDD as the outcomes. We expect a startle by time interaction such that regardless of treatment arm, a change in U-threat reactivity will correspond to a change in drinking behavior.

Sample Size. Our key hypothesis testing involves treatment arm by session interactions on startle eyeblink potentiation. Assuming a medium to large effect size, which is supported by our preliminary data, a sample size of 40 individuals per treatment group would conservatively yield 91% power (a total sample size of 80 individuals). To account for potential screen-fails, participants requesting to drop out of the study, and the PI withdrawing participants due to meeting termination criteria, approval for 120 participants is requested.

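### Replacing Bonferroni with Holm over the same set of tests keeps the same familywise error control and can only add power to the key startle tests

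*Combined protocol and SAP*

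**What the plan says.** The only general multiplicity rule is one sentence in section 10.0, Quality Control and Quality Assurance, placed after the text on self-report data handling: "Type 1 error rates will be adjusted using Bonferroni corrections". It gives no overall alpha, number of tests or list of tests covered. The fMRI maps have a separate familywise correction, described in section 6.0.

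Section 12.0, Statistical Considerations, does not mention multiplicity. Its sample-size paragraph identifies what matters most: "Our key hypothesis testing involves treatment arm by session interactions on startle eyeblink potentiation". Two analyses fit that description:

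- **H1**, baseline against acute challenge, where "we expect a time x treatment arm x task condition interaction on startle".
- **H2a**, baseline against post-treatment, where "we will conduct a multilevel mixed model that is nearly identical to the model described for H1".

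On power, the paragraph says: "Assuming a medium to large effect size, which is supported by our preliminary data", and that "a sample size of 40 individuals per treatment group would conservatively yield 91% power". It states no alpha, sidedness or numeric effect size.

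**The concern.** Bonferroni tests every hypothesis in the family at alpha divided by the number of tests, whatever the other tests show. Holm begins at the same threshold but relaxes it after each rejection. For two tests, the smaller p-value must be at or below 0.025. If it is, the larger need only be at or below 0.05. Familywise error is still held at 0.05 under any dependence between the tests. That matters here because H1 and H2a share participants and the same baseline measurement.

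The trial expects effects on both tests, since it asks about an acute dose and about daily use. Finding both is therefore a result the investigators care about, and it is where Bonferroni loses most against Holm. The plan gives up this power and gains no extra protection against false positives.

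**Working it through.** **Inputs.** From the sample-size paragraph: 40 per arm and 91% power. Assumed, because the documents do not say: two-sided alpha 0.05, the same effect size for H1 and H2a, and a correlation between the two test statistics of 0 to 0.5.

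**The plan's own figure.** With n per arm and standardised between-arm difference in change d, the normal approximation is

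power = Φ(d·√(n/2) − z), where √(40/2) = 4.472 and z = 1.960 at two-sided 0.05.

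- d = 0.5: Φ(2.236 − 1.960) = 60.9%
- d = 0.65: Φ(2.907 − 1.960) = 82.8%
- d = 0.8: Φ(3.578 − 1.960) = 94.7%

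So 91% cannot be reproduced from what is stated. Solving backwards, d = (1.960 + 1.341)/4.472 = 0.738. A noncentral-t calculation gives 0.747.

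**Bonferroni, two tests.** Each is tested at 0.025, so z = 2.241. Power per test = Φ(3.301 − 2.241) = Φ(1.059) = 85.5%. The noncentral t gives 85.2%.

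**Holm, two tests, both effects real, correlation 0.** Let a = 0.9100 (power at 0.05) and b = 0.8553 (power at 0.025).

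- Per test: b + (a − b)·b = 0.8553 + 0.0547 × 0.8553 = 90.2%.
- Both significant: a² − (a − b)² = 0.8281 − 0.0030 = 82.5%. Bonferroni: b² = 73.2%.
- At least one: 1 − (1 − b)² = 97.9% under either method, because both use 0.025 for the smaller p-value.

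**Holm, two tests, one effect real, correlation 0.** Power for the real effect is 0.8553 + 0.0547 × 0.025 = 85.7%, a gain of 0.14 points.

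A simulation with 400,000 draws agrees with these and covers correlation 0.5:

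| H1 and H2a | Bonferroni | Holm |
|---|---|---|
| Both real: power per test | 85.5% | 89.4-90.3% |
| Both real: both significant | 73.2-76.6% | 82.6-84.3% |
| Both real: at least one significant | 94.5-97.9% | 94.5-97.9% |
| One real: power for that test | about 85.5% | 85.6-85.8% |
| Neither real: any false rejection | 4.7-5.0% | 4.7-5.0% |

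Ranges run over correlations 0 and 0.5. In the last row both methods give the same value in each run.

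**A larger family.** Suppose the two drinking outcomes of H3a are also covered, making four tests. Bonferroni power for each startle test is Φ(3.301 − 2.498) = 78.9%. Holm gives 80.9-81.4% if neither drinking effect is real. It gives 86.5-88.6% if all four are real with equal power. The second case is illustrative only, since the plan states no power for drinking outcomes.

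**Whether 91% already allows for adjustment.** At alpha 0.025 and d = 0.80, power is Φ(3.578 − 2.241) = 90.9%. The stated figure therefore also fits a calculation that already includes a two-test Bonferroni.

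**The case against.** The strongest reply is that Bonferroni is valid and simple, and that Holm's advantage depends on several effects being real. This is right as far as it goes. With one real effect the gain is negligible, the chance of at least one positive result never changes, and Holm does not restore 91% in any case above. Bonferroni also has simple matching simultaneous confidence intervals, which Holm lacks, but the plan calls for none. What remains is that Holm is never worse for testing.

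A reader might infer more than the documents support:

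- **That Bonferroni makes the stated 91% too high.** This cannot be settled. The plan gives no alpha, and 91% is compatible with an already adjusted 0.025 and a large effect.
- **That Bonferroni is applied to an unlimited list of tests.** The sentence lists none, and its position could mean that it was written with the self-report data in mind. The missing list is missing detail, and either procedure needs it.
- **That the remedy is a short family, with H2b, H3b and H3c moved to exploratory status.** In the Aims and in section 12.0, only the Aim 2 fMRI work is called exploratory. Leaving stated hypotheses unadjusted gains power by giving up protection, and that is a scientific choice. Splitting has the same drawback. With all nulls true, separate Holm pairs for startle and drinking give an 8.2-9.6% chance of a false claim across the four tests, against 4.3-4.9% for Bonferroni over all four. At correlation 0, these are 1 − 0.975⁴ = 9.6% and 1 − 0.9875⁴ = 4.9%.

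**Conclusion.** The point holds as an improvement in method. On an unchanged family, Holm gives the same familywise protection as Bonferroni and at least equal power. For H1 and H2a with both effects real, the gain is about 4 to 5 points per test and about 8 to 9 points for both being significant. With one effect real it is about 0.2 points. These sizes rest on each test having 91% power at two-sided 0.05 (d about 0.74) and on correlations of 0 to 0.5, none of which the plan states. That Holm is never less powerful rests on none of these assumptions. The choice of Bonferroni is not an error, and an overstatement of power is possible but not shown.

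**What to change.** Replace the sentence in section 10.0 with Holm's step-down procedure at a familywise two-sided 0.05. Apply it to the same set of tests that Bonferroni would have covered, and list that set. It should include at least the startle tests for H1 and H2a. Do not divide the set into separate families or remove hypotheses from adjustment in order to gain power.

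In the sample-size paragraph, state the alpha, sidedness and numeric effect size behind the 91%. If that figure was computed at an unadjusted 0.05, restate it at the adjusted level. For two tests under the assumptions above, that is 85.5% per test at the first Holm step and 89-90% if both effects are real.

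The cost is one rewritten sentence and a clarified power statement, settled before unblinding. No participants, visits or measurements are added and no error control is lost, so this is a free improvement. The restated power may look slightly less favourable.

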- Following the Screening Session, eligible participants will be randomized to a treatment group (i.e., SUV or placebo) and protocol arm (i.e., EMG/EEG only or EMG/EEG + fMRI). Treatment group randomization will be double-blinded.
- Research study staff will monitor the participants throughout the course of the research to ensure that they still meet eligibility criteria, and their continuing eligibility will be documented by the research staff. This will include ensuring abstinence from alcohol at both laboratory visits. It will also ensure that no participant is pregnant at either session.
- Upon enrollment into the study, participants will be required to agree and consent to not operating heavy machinery, including driving a vehicle, for at least 24-hours after the Acute Drug Challenge visit due to day-time drug administration.
- Participants will also be instructed that they will be required to fast for at least 2-hours prior to the Acute Drug Challenge visit to avoid interactions between food and SUV metabolism. The Acute Drug Challenge visit will therefore begin at approximately 9-10am.
- Following the Acute Drug Challenge visit, participants will be instructed to take either SUV or placebo, dependent upon their randomized treatment group, once daily before bed for 4 weeks. Participants will complete daily online clinical assessments. The PI and study staff will monitor potential side effects and drug adherence throughout the duration of the 4 weeks.
- Participants will return to the lab at the end of the 4 weeks and complete a third EMG/EEG, and second fMRI (dependent upon randomization).
- Participants will be debriefed and provided AUD treatment referrals as appropriate at the end of their study participation.

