Randomization, Blinding, and Dosing. A computerized stratified block randomization will assign subjects to a treatment group and protocol arm. The randomization will be stratified by biological sex. The research team and participants will be blind to medication assignment. The PI will have the ability to unblind if needed. OSU Investigational Drug Services (IDS) staff and CRC medical staff will be unblinded.

Participants will receive either placebo or suvorexant (Belsomra®; 10mg; Merck & Co). This dose was chosen because it is the lowest clinical dose for sleep and arousal-related outcomes. We used 10mg in our pilot project and found significant change in reactivity to U-threat without adverse reactions (Protocol#: 2020H0285).

Laboratory Tasks. Participants will complete a startle response to threat task at the EMG/EEG, fMRI, and Acute Drug Challenge Visits (described below). The same paradigm will be administered during the EMG/EEG and Acute Drug Challenge Visit. The fMRI task is analogous to the original design; however, shock is administered to the left foot to minimize potential scanner interference and individual shock levels are re-calibrated. During the tasks, we will collect psychophysiological measures including startle eyeblink potentiation. At the EMG/EEG visit a second task, Alcohol Cue Reactivity⁷¹ will be completed. These tasks are well-established, validated paradigms,

previously used in our laboratory for the past several years in both healthy and adults with AUD.

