Discovery and disclosure of incidental finding or abnormality on MRI scans: During the formal consent process, all subjects will be informed about the potential risks of discovering an incidental finding or abnormality on their MRI scan. The Center for Cognitive and Behavioral Brain Imaging is a research center. It is NOT a Clinical MRI facility in a hospital. There are no neuroradiologists at the Center for Cognitive and Behavioral Brain Imaging, therefore the staff are unable to make any medical comments on the scans. However, all structural scans obtained in normal research subjects are sent to a neuroradiologist for review. In addition, participants are given the structural images on a CD. In the event the neuroradiologist detects an abnormality, the Center staff will forward his findings to the participant primary care physician (PCP) within one month of the scan. The participant and PCP will receive information that the neuroradiologist has found some abnormalities that could be potentially significant. This will be communicated by a letter. The neuroradiologist will be available to consult with the PCP if it is necessary. Any costs associated with seeing the primary care physician will be participant responsibility. If participants cannot designate a primary care physician in the MRI Screening Form, they cannot participate in the study. Normal scan results will be available one month after the study and will not be communicated to a primary care physician.

Suvorexant-Related Risks: Suvorexant is a Drug Enforcement Administration (DEA) schedule IV-controlled substance in the United States because it is considered to have abuse liability similar to other approved sleep medications (e.g., zolpidem). Preclinical self-administration studies in rats and monkeys indicate suvorexant does not have positive reinforcing effects⁶⁵. In previous clinical trials there has been no evidence of physical dependence with the prolonged use⁶⁶. There is also no evidence of withdrawal or “discontinuation syndrome” following abrupt discontinuation⁶⁶.

Suvorexant is associated with some potential adverse side-effects including: sleepiness or drowsiness, headache, nausea, dizziness, diarrhea, dry mouth, and abnormal dreams. Next day drowsiness is considered the most common side-effect. All

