- Weekly meetings of the research staff of this study will be conducted that will include review of accrual, consenting procedures, protocol adherence, adverse events, and quality control of all data obtained from the study in the previous week. All changes in protocol design will be reviewed by the IRB before such changes in protocol design take place.
- All AEs occurring during the course of the study will be reported to the PI. Serious adverse events (SAEs) will be reported by the PI to the IRB within 5 business days of the PI (or her team's) knowledge of the SAE. Moderate adverse events (AEs) that are unexpected and indicate that the research is associated with a greater risk of harm to participants or others than previously known will be reported to the IRB within 15 business days of the PI's (or her team's) knowledge of the event. All mild AEs and moderate AEs that are expected or are not associated with a greater risk of harm to participants or others than previously known will be reported to the IRB at the scheduled Continuing Review.

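### Blink files are accepted or rejected by hand by a team that also sees side-effect data, and the plan does not mask participant or visit or lock the edits before unblinding

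*Combined protocol and SAP*

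**What the plan says.** Section 12.0 (Aims 1 and 2) models startle magnitude and looks for a time by arm by task-condition interaction. Section 6.0, under Startle Data Collection and Processing, sends the mean blink magnitude per condition into the primary analyses. No endpoint is formally labelled primary, but the Sample Size paragraph rests on startle.

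Section 6.0 sets a blink to missing when the baseline period is contaminated by noise, when there is movement artifact, or when a spontaneous or voluntary blink begins too early. No numeric threshold is given for noise or movement. The processing program is described as interactive in sections 6.0 and 9.0. Section 10.0 says scripts process the data, but that "the PI and study staff examine each blink file by hand to ensure acceptability and high-quality data".

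On blinding, section 6.0 says "The research team and participants will be blind to medication assignment", then "The PI will have the ability to unblind if needed" and "OSU Investigational Drug Services (IDS) staff and CRC medical staff will be unblinded".

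On side effects, section 5.0 says "The PI and study staff will monitor potential side effects and drug adherence throughout the duration of the 4 weeks". Section 11.0 says "All AEs occurring during the course of the study will be reported to the PI", and its weekly staff meeting reviews "adverse events, and quality control of all data obtained from the study in the previous week". Section 7.0 says "Next day drowsiness is considered the most common side-effect". At the acute challenge, sleepiness and drug-effect ratings are taken nine times, including at 90, 120 and 150 minutes, around the laboratory test at about 2 hours.

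Task files are saved under the participant's research identifier (section 8.0).

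**The concern.** A formal blind stops the scorer from being told the arm. It does not stop the scorer from forming a view of the arm from sleepiness, reported side effects or adverse event discussions. If the person deciding whether a blink counts holds such a view, and expects less U-threat startle on drug because the team's own pilot found it, decisions near the margin can lean one way in one arm. This differs from random loss of blinks. Section 9.0 relies on a large number of probes to keep missing responses from biasing the analysis, but more probes do not remove bias from selective rejection.

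At stake is how defensible the startle result is. It is meant to inform and power a larger trial, and once files have been scored with participant and visit visible, a reader can exclude this explanation only if they are scored again.

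**Working it through.** **Step 1. Does anything separate the two streams of information?**

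| Question | What the plan provides |
|---|---|
| Who examines blink files? | PI and study staff, every file (10.0) |
| Who follows side effects? | PI and study staff (5.0); all adverse events go to the PI (11.0) |
| Where do the streams meet? | One weekly meeting covers adverse events and data quality (11.0) |
| Is the rejection rule mechanical? | Partly: scripts first, then hand review under qualitative criteria (6.0, 10.0) |
| Is participant or visit hidden from the scorer? | Not stated; files carry the participant identifier (8.0) |
| Are edits logged, or locked before unblinding? | Not stated |
| Does someone who unblinds stop scoring? | Not stated |
| Second scorer or agreement check? | Not stated |

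The PI is named in both roles. For other staff the overlap is one of role, not shown for individuals.

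**Step 2. The plan's nearest figure.** The Sample Size paragraph gives 91% power with 40 per arm for a medium to large effect, with no number, alpha or correlation. For a two-arm comparison of change scores at two-sided 5% (assumed), power ≈ Φ(d·√(40/2) − 1.96). This equals 91% at d = (1.96 + 1.34)/4.47 = 0.74, which lies inside 0.5 to 0.8 if that is what medium to large means. The 91% can be neither confirmed nor refuted, and the point does not depend on it. It only gives a scale.

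**Step 3. How much false shift can the test tolerate?** The standard error of the arm difference, in SD of change, is √(2/40) = 0.224. For a false shift b, the two-sided type I error is 1 − Φ(1.96 − b/0.224) + Φ(−1.96 − b/0.224).

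| b (SD of change) | Type I error |
|---|---|
| 0 | 5.0% |
| 0.05 | 5.6% |
| 0.10 | 7.3% |
| 0.20 | 14.5% |
| 0.30 | 26.9% |

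Every non-zero b is an assumption; the documents give none.

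**Step 4. What would produce such a shift?** At 20 probes per condition and about 7% missing, 0.07 × 20 = 1.4 blinks per condition are lost. (Section 9.0 says 72 probes, not 60; at 24 per condition this is 1.7. The two counts should be reconciled.) In a normal sample of 20 the largest value averages 1.87 SD above the mean, so dropping it lowers the mean by 1.87/19 = 0.098 trial-level SD. Simulation gives the same value, and 0.136 for a right-skewed lognormal with log-SD 0.6.

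If the trial-level SD is 1 to 2 times the SD of change (assumed), the ceiling is 0.098 × 1 = 0.10 to 0.136 × 2 = 0.27 SD. That requires dropping the single largest U-threat blink, after dosing only, in every drug participant and in no placebo participant.

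If instead the scorer acts on a guess that is right 65% of the time (assumed), the between-arm difference is multiplied by 0.65 − 0.35 = 0.30. The shift becomes 0.03 to 0.08 SD, and by the table the type I error stays below 7.3%.

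**The case against.** The strongest reply is that the safeguards in place are substantial. The team is blind by protocol, scripts do the processing, the rejection criteria concern mainly the period before the response and do not mention blink size, and scoring follows published guidelines. The pilot at this dose is reported as free of adverse reactions, daily dosing is at bedtime, and no drowsiness rate is given. For H1, the baseline file precedes any dose. If files are scored soon after each session, the acute file also precedes most side-effect reports. Rejections spread over U-threat and P-threat would largely cancel in the interaction.

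Most of this stands, and it limits the likely size. It does not close the gap. The plan does not date the scoring, the sleepiness and drug-effect ratings fall around the acute test itself, and H2a uses a file recorded after four weeks of side-effect monitoring. The scripts are followed by hand review.

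It could also be said that renaming files leaves trial condition visible. That does not defeat the fix. A scorer who cannot tell participant or visit cannot apply a guess at the arm, so any leaning by condition is not steered by arm.

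**Conclusion.** The gap is real but modest. Hand acceptance of blinks is not separated from information that could suggest the arm, and the plan has no masking of participant or visit, no edit lock and no recusal rule. This calls for a cheap improvement; it does not show that the endpoint is compromised.

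Several stronger readings go beyond the documents:

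- A reader might infer that scorers know the arm, or will often guess it. The team is formally blind, and no drowsiness rate supports the word often.
- A reader might take 0.1 to 0.3 SD as the expected bias. That is the ceiling in the working, under extreme and one-sided behaviour. The documents do not show that any bias would occur.
- A reader might see the PI's ability to unblind as the flaw. It is an ordinary safety provision; what is missing is a rule about scoring after it is used.
- A reader might place the PI at the tasks. Section 7.0 says only that the PI or co-investigator is available.
- A reader might extend the point to fMRI motion. Section 6.0 already gives a numeric cut-off there (more than 1.5 mm).

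The size figures rest on a two-sided 5% test, 40 analysed per arm, an assumed SD ratio and an assumed guessing accuracy.

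**What to change.** In section 6.0 (Startle Data Collection and Processing) and section 10.0, state that:

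- blinks are accepted or rejected on files renamed by script with a random code that hides participant and visit;
- every edit is logged, and edits are locked before the codes are linked back;
- same-day review after a session checks only that the recording is complete;
- anyone who has unblinded a participant does not score that participant's files.

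Leave the PI's emergency unblinding as it is; moving it would alter a safety pathway and is not needed for this purpose.

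The cost is a renaming script and a few sentences of protocol text, with no extra staff and no change to dosing, visits or safety monitoring. The one drawback is that scoring runs in batches rather than straight after each session.
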